### **Systemic Lupus Erythematosus Responder Index (SRI-4)**

A subject achieves SRI-4 response if all of the following criteria are met:

1.  $\geq 4$ -point reduction from baseline in hSLEDAI score
2. no new BILAG 2004 A and no  $> 1$  new BILAG 2004 B domain scores compared with baseline (e.g. no B, C, D or E scores at baseline becomes an A or no more than 1 C, D or E score at baseline becomes a B)
3.  $< 0.3$ -point deterioration from baseline in PGA VAS (scale 0 to 3).
4. no use of more than protocol-permitted therapies (i.e. requiring a dose of systemic steroid [for e.g., OCS or intravenous [IV] or intramuscular [IM] corticosteroid] above their baseline dose after week 16; requiring either dose increases of the current immunosuppressants/immunomodulators or initiation of new immunosuppressant/immunomodulatory(s)).

The latest visit date among hSLEDAI, BILAG and PGA VAS will be considered the SRI-4 visit date. In the case when all three visit dates are missing, the upper limit of the analytic window of this visit will be the SRI-4 visit date.

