2.3.1 COVID-19

Amgen closely monitors the coronavirus disease 2019 (COVID-19) pandemic around the world. As part of this effort, Amgen performs a rigorous assessment, considering the study design, patient safety, public health risk, benefit-risk assessment, as well as the burden on country healthcare systems. Decisions are made on a study-by-study and country-by-country basis to minimize risk to subjects and avoid undue burden on healthcare facilities.

Subjects who display symptoms consistent with COVID-19 infections or who have tested positive for COVID-19 should contact the investigator to ensure appropriate care as well as documentation and management of study activities. Amgen considers that it is important to continue the proposed development of efavaleukin alfa in this study in order to advance potential therapy options for patients as rapidly as possible, while balancing this with appropriate measures to monitor and mitigate the potential impact of COVID-19. Subjects enrolled in this study are permitted to receive vaccinations for COVID-19 except as described in exclusion criterion 220 and Section [6.1.6](#).

[figure not shown]
3. Objectives and Endpoints/Estimands

[figure not shown]
Objectives	Endpoints
Primary	
• Evaluate the efficacy of efavaleukin alfa at week 52, as measured by the SRI-4 response	• SRI-4 response at week 52
Primary Estimand	
The primary estimand is the difference in SRI-4 response rates between each efavaleukin alfa dose group and placebo at week 52 for all subjects with SLE with inadequate response to SOC therapy who are randomized, regardless of investigational product compliance; subjects will be considered nonresponders for using more than protocol-permitted therapies as follows:	

Subjects requiring a dose of systemic corticosteroids for SLE above their baseline dose after week 16Subjects requiring either dose increases of the current immunosuppressants/immunomodulators or initiation of new immunosuppressant/immunomodulator(s)	
Secondary	
• Evaluate the efficacy of efavaleukin alfa at week 52, as measured by the BICLA index responses	• BICLA response at week 52
• Evaluate the efficacy of efavaleukin alfa at week 52, as measured by LLDAS response	• LLDAS response at week 52
• Evaluate the efficacy of efavaleukin alfa at week 52, as measured by OCS tapering	• Reduction of OCS to \leq 7.5 mg/day by week 44 and sustained through week 52 in subjects with a baseline OCS dose \geq 10 mg/day

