6.1.3.2 Oral Corticosteroids

Subjects who are taking OCS prior to screening should remain on a stable dose of OCS between \geq 2 weeks prior to screening through week 12, with some exceptions as defined below. Initiation or temporary increases in the OCS dosage is not encouraged but are allowed if initiated at any time between day 1 and week 10 with a return to baseline dose within the subsequent 2 weeks. In such cases, initiation or temporary increase of OCS is limited to a dose \leq 5 mg/day of prednisone (or equivalent).

Subjects may begin tapering OCS after the week 12 assessment up to the week 44 assessment with initiation of tapering based upon clinical judgement of the treating physician. The tapering schedule should be directed at the discretion of the investigator but should generally not be tapered more than 20% of the prior dose per week. Tapering OCS before week 12 is not encouraged but may be allowed based upon investigator's judgement. Between weeks 44 and 52, the OCS dosing must again remain stable.

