6.7.2 Concomitant Treatment

Throughout the study, investigators may prescribe any concomitant medications or treatments deemed necessary to provide adequate supportive care except for those listed in Sections 6.1.3 and 6.1.6.

Concomitant therapies (including vaccines) are to be collected from randomization through the end of the safety follow-up period. For concomitant therapies, collect therapy name, indication, dose, unit, frequency, start date, and stop date. Guidelines for immunomodulators, immunosuppressants, and OCS are provided in Section [6.1.3](#).

7. Discontinuation of Study Treatment and Subject Discontinuation/Withdrawal

Subjects have the right to withdraw from investigational product and/or other protocol-required therapies, protocol procedures, or the study as a whole at any time and for any reason without prejudice to their future medical care by the physician or at the institution.

The investigator and/or sponsor can decide to withdraw a subject(s) from investigational product, device, and/or other protocol-required therapies, protocol procedures, or the study as a whole at any time prior to study completion for the reasons listed in Section [7](#).

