## 2. Objectives, Endpoints and Hypotheses

### 2.1 Objectives and Endpoints/Estimands

[figure not shown]
Objectives	Endpoints
Primary	

Evaluate the efficacy of efavaleukin alfa at week 52, as measured by the SRI-4 response

	

SRI-4 response at week 52

Primary Estimand	
The primary estimand is the difference in SRI-4 response rates between each efavaleukin alfa dose group and placebo at week 52 for all subjects with SLE with inadequate response to SOC therapy who are randomized, regardless of investigational product compliance; subjects will be considered non-responders for using more than protocol-permitted therapies including: 

Subjects requiring a dose of systemic corticosteroids for SLE above their baseline dose after week 16

Subjects requiring either dose increases of the current immunosuppressants/immunomodulators or initiation of new immunosuppressant/immunomodulator(s)

	
Secondary	

Evaluate the efficacy of efavaleukin alfa at week 52, as measured by the BICLA index responses

	

BICLA response at week 52

Evaluate the efficacy of efavaleukin alfa at week 52, as measured by LLDAS response

	

LLDAS response at week 52

Evaluate the efficacy of efavaleukin alfa at week 52, as measured by OCS tapering

	

Reduction of OCS to <math>\leq 7.5</math> mg/day by week 44 and sustained through week 52 in subjects with a baseline OCS dose <math>\geq 10</math> mg/day

Evaluate the efficacy of efavaleukin alfa at week 24, as measured by SRI-4 response

	

SRI-4 response at week 24

Evaluate the efficacy of efavaleukin alfa at week 24, as measured by the BICLA index responses

	

BICLA response at week 24

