**Exploratory**

**2.2 Hypotheses and/or Estimations**

At least 1 efavaleukin alfa dose will have greater efficacy than placebo as measured by the SRI-4 response rate at week 52 in subjects with active SLE with inadequate response to SOC therapy who are randomized, regardless of investigational product compliance; subjects using more than protocol-permitted therapies will be considered as non-responders:

- Subjects requiring a dose of systemic corticosteroids for SLE above their baseline dose after week 16
- Subjects requiring either dose increases of the current immunosuppressants/immunomodulators or initiation of new immunosuppressant/immunomodulator(s).

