Immunosuppressant/immunomodulator dose(s) should remain stable through week 52. For OCS, initiation or temporary increases in OCS are allowed between weeks 0 to 10, provided that return to baseline dose occurs within the subsequent 2 weeks. OCS may be tapered after week 12 at the investigator's discretion but should not be changed during the last 8 weeks (week 44 to 52) of the 52-week treatment period.

Subjects who meet the criteria listed below will be allowed to continue the study but will be considered as experiencing treatment failure for the primary efficacy endpoint analyses:

- Subjects requiring a dose of systemic corticosteroids for SLE above their baseline dose after week 16
- Subjects requiring either dose increases of the current immunosuppressants/immunomodulators or initiation of new immunosuppressant/ immunomodulator(s)

IAs will be conducted to allow for adaption of the randomization ratio for newly enrolled subjects to the 3 efavaleukin alfa treatment groups, holding the allocation to placebo

constant at 25%, and assessing efficacy for early futility or administrative success decisions:

- The study team, investigators, and subjects will remain blinded to the results of the IAs unless futility is determined.
- The first IA will be executed after the first 40 subjects are randomized and have had the opportunity to complete the week 24 assessment. Subsequent IAs are scheduled after every additional 32 subjects are randomized and have had the opportunity to complete the week 24 assessment until full enrollment or until futility is determined for all doses at an IA. The last IA will occur when all 320 subjects are randomized and have had the opportunity to complete the week 24 assessment. This IA will be referred to as the 'all-subjects-week-24 IA'. Analyses planned at each IA are listed in [Table 3-1](#).
- Efficacy analyses will be performed at the IAs to assess the likelihood of each efavaleukin alfa treatment group being superior to placebo by a clinically meaningful difference.
  - From the second IA until before the last IA, if this likelihood is unacceptably low for all dose levels, the trial is recommended to stop for futility.

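### SRI-4 criterion 4 in SAP 5.6 drops the SLE limit on steroid use that the primary estimand carries, so the derived endpoint does not match the stated estimand

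*SAP*

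**What the plan says.** **Derivation.** SAP 5.6 gives SRI-4 four criteria. The fourth is no use of therapies beyond those the protocol permits. It is spelled out after an i.e. as "requiring a dose of systemic steroid [for e.g., OCS or intravenous [IV] or intramuscular [IM] corticosteroid] above their baseline dose after week 16", together with increases or starts of immunosuppressants or immunomodulators. No indication is stated. The protocol's own SRI-4 definition (8.2.9.8) has only the hSLEDAI, BILAG and PGA components, so the medication rule enters the derivation in SAP 5.6.

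**Estimand.** SAP 2.2 words the steroid event as "Subjects requiring a dose of systemic corticosteroids for SLE above their baseline dose after week 16". SAP 3.1 has the same item in a list introduced by "Subjects who meet the criteria listed below will be allowed to continue the study but will be considered as experiencing treatment failure". The protocol's primary estimand (Sections 1.1 and 3) has it after "subjects will be considered nonresponders for using more than protocol-permitted therapies as follows". SAP 2.1 repeats the item but opens its list with "subjects will be considered non-responders for using more than protocol-permitted therapies including". Protocol 7.1, on keeping subjects in the study, also ties the oral steroid event to SLE.

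**Data.** Protocol 6.7.2 states: "For concomitant therapies, collect therapy name, indication, dose, unit, frequency, start date, and stop date". The indication needed to apply the limit is therefore recorded.

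**The concern.** The estimand says which post-randomization events count as failure, and the derivation should apply those events and no others. Here the derivation applies a wider one. Take a subject who meets the three disease criteria at week 52 and who had a course of systemic steroid above baseline after week 16 for a condition other than SLE. That subject is a non-responder under SAP 5.6 and a responder under the lists in SAP 2.2, SAP 3.1 and the protocol.

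The affected outputs are the SRI-4 counts and percentages at weeks 52 and 24 (SAP Tables 9-1 and 9-2), the subgroup summaries (SAP 4.2), and the investigator-adjudicator concordance tables, where a week 52 rate below 0.95 may lead to a sensitivity summary (SAP 9.5). The routine exposure outputs would not show which rule was used. SAP 9.6.7 summarizes only baseline exposure to oral steroid and immunosuppressants, and SAP 9.6.8 drops concomitant medication exposure. The deviation table and list in SAP 9.3 might capture barred IV or IM steroid, but the deviation categories are not given.

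**Working it through.** The plan states no figure on this point, so there is none to reproduce. The check compares the texts and then works an illustration of size.

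**Texts side by side**

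| Place | List form | Steroid limited to SLE? |
|---|---|---|
| SAP 5.6, SRI-4 criterion 4 | closed (i.e.) | no |
| SAP 5.6, BICLA criterion 5 | closed (i.e.) | no |
| SAP 2.2 | closed (colon, two items) | yes |
| SAP 3.1 | closed (refers to the criteria that follow) | yes |
| Protocol 1.1 and 3, primary estimand | closed (as follows) | yes |
| SAP 2.1 | open (including) | yes |

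All of these start the steroid event after week 16, so they differ only on indication. No passage says that criterion 4 is to be read with the SLE limit. SAP Section 10 lists key changes from the protocol, and dropping the limit is not among them.

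**Size, week 52.** Let q be the share of an arm with non-SLE systemic steroid above baseline between weeks 16 and 52. The documents do not give q; 1% to 6% is an assumption. Exclusion criterion 204 selects against such use but does not rule out later acute use. Let p be the arm's SRI-4 rate under the estimand rule, here 40%, the design placebo rate (SAP 3.2). If use is independent of response, the arm's rate falls by q × p:

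- q = 1%: 0.01 × 0.40 = 0.4 points
- q = 2%: 0.02 × 0.40 = 0.8 points
- q = 4%: 0.04 × 0.40 = 1.6 points
- q = 6%: 0.06 × 0.40 = 2.4 points

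**Size, week 24.** Of the 36 weeks from 16 to 52, 8 have passed. At a constant rate, q is 8/36 of the above and the shift is about 0.1 points (0.4 × 8/36 = 0.09) to 0.5 points (2.4 × 8/36 = 0.53).

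**Difference between arms.** With equal q, the difference falls by q × (p1 − p0):

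- no true effect: 0 points
- 15-point effect (the futility margin): 0.01 × 15 = 0.15 to 0.06 × 15 = 0.9 points
- 25-point effect (the design value): 0.01 × 25 = 0.25 to 0.06 × 25 = 1.5 points

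With unequal use the shift is q1 × p1 − q0 × p0. At the ends of the assumed range, with both arms at 40%, that is 0.06 × 0.40 − 0.01 × 0.40 = 2.0 points.

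**Concordance.** SAP 9.5 sends assessment scores, not medication records, to adjudication. If criterion 4 is applied alike to both sources, a subject it makes a non-responder counts as agreement. The wider rule can then only raise the concordance rate or leave it unchanged.

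**The case against.** The strongest reply is that the SAP leaves no real doubt about what to program. SAP 5.6 is the definition section, and SAP 8.3 tells the programmer to evaluate the SRI-4 criteria; SAP 2.2 is a hypothesis statement and SAP 3.1 a design overview. The protocol's amendment 2 summary adds that detail was taken out of the estimand wording because the SAP would specify it. Part of this stands: a reader might infer that the programmer has no guidance, and that goes too far. But guidance that contradicts the estimand is still a contradiction. The same amendment entry says that the principle for handling these events is unchanged, and the SLE limit is still in the current estimand text.

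A second reply is that non-SLE steroid is outside the permitted therapies anyway. Protocol 6.1.3.2 says that temporary oral steroid increases "are allowed if initiated at any time between day 1 and week 10 with a return to baseline dose within the subsequent 2 weeks", with no exception by indication. Protocol 6.1.6 bars IV and IM steroid. Protocol 6.7.2 says that "investigators may prescribe any concomitant medications or treatments deemed necessary to provide adequate supportive care except for those listed in Sections 6.1.3 and 6.1.6". A reader might infer that the documents support the two rules equally. They do not, because these are conduct rules and do not define failure. An oral increase started between weeks 10 and 16, or IV steroid before week 16, falls outside them, yet no list counts it as steroid failure.

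A third reply is that this is a wording slip in a descriptive analysis and so a minor edit. The smallness of the edit and the descriptive setting are both granted. But the endpoint is the primary one, and the reported percentages depend on which section is followed.

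**Conclusion.** The mismatch is real. SRI-4 as defined in SAP 5.6 applies a wider steroid failure event than the protocol's primary estimand and SAP 2.2 and 3.1, and the change is not recorded. It should be corrected, but its weight is modest. The final analysis has no treatment comparison (SAP Section 10), and the size cannot be derived from the documents. Under the assumed 1% to 6%, independent of response, a 40% arm rate moves by 0.4 to 2.4 points at week 52; with equal use across arms the difference moves by at most 1.5 points at the design effect.

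Two stronger readings are not supported. A reader might infer that the wider rule counts against the active arms, because the protocol lists hypersensitivity and rash among adverse drug reactions (Sections 1.1 and 2.3) and these might be treated with steroid. That is possible, and equal use is only an assumption, but the documents give no frequency of such treatment by arm. A reader might also infer that the futility decision was affected. The documents do not say which rule was programmed at the interim analyses and give no data from which to judge.

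**What to change.** Reconcile the passages so that one event list serves both the estimand and the derivation. The direct way is to align SRI-4 criterion 4 with the protocol estimand by adding the SLE limit and applying it through the recorded indication. State in the same place how oral, IV and IM steroid given for a non-SLE reason is handled.

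If the wider rule was intended, record it in SAP Section 10 as a departure from the protocol estimand and bring SAP 2.1, 2.2 and 3.1 into line. This is not an equal alternative: it would widen the failure event after the futility result and move the SAP away from the protocol.

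BICLA criterion 5 has the same wording. Check it for consistency, and against Protocol 8.2.9.11, which words its treatment condition differently, as no start of non-protocol treatment.

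The cost is a few words in the SAP and a filter on a field already collected. Some recorded indications may need review before database lock.

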### **BILAG-based Composite Lupus Assessment (BICLA)**

A subject achieves BICLA response if all of the following criteria are met:

1. at least one gradation of improvement in baseline BILAG domain scores in all body systems with moderate or severe disease activity at entry (e.g., all A (severe disease) domain scores at baseline falling to B (moderate), C (mild), or D (no activity), and all B domain scores at baseline falling to C or D)
2. no new BILAG 2004 A domain score and no  $> 1$  new BILAG 2004 B domain scores compared with baseline
3. no worsening of the hSLEDAI score from baseline
4.  $< 0.3$ -point deterioration from baseline in PGA VAS (scale 0 to 3)

5. no use of more than protocol-permitted therapies (i.e. requiring a dose of systemic steroid [for e.g., OCS or IV or IM corticosteroid] above their baseline dose after week 16; requiring either dose increases of the current immunosuppressants/immunomodulators or initiation of new immunosuppressant/immunomodulatory(s)).

### **PGA – 4-Point Verbal Rating Scale**

The PGA 4-Point Verbal Rating Scale uses 4 verbal descriptors for assessing the severity of disease since the last visit. The options for disease severity are none, mild, moderate, and severe.

This is a global assessment, factoring in all aspects of the subject's lupus disease activity. It should not reflect non-lupus medical conditions. This assessment will be completed by a health care provider (HCP) and must be done before assessing the hSLEDAI and BILAG.

### **Swollen and Tender Joint Count**

Joints that have been replaced during the study, or have trauma or received intra-articular injections are considered non-evaluable throughout the study.

Swollen Joint Count Assessments – A total 28 joints will be scored for presence or absence of swelling. A separated score for joints in the hands and wrists will be calculated.

Tender Joint Count Assessments – A total 28 joints will be scored for presence or absence of tenderness. A separated score for joints in the hands and wrists will be calculated.

Swollen and Tender Joint Count Assessments: joints in hands and wrists will be scored for the simultaneous presence or absence of swelling and tenderness.

### **Cutaneous Lupus Erythematosus Area and Severity Index (CLASI)**

The CLASI consists of 2 scores, the first summarizes the activity of the disease while the second is a measure of the damage done by the disease. Activity is scored based on erythema, scale/hyperkeratosis, mucous membrane involvement, acute hair loss and non-scarring alopecia. Damage is scored in terms of dyspigmentation and scarring, including scarring alopecia. Subjects are asked whether dyspigmentation due to cutaneous lupus lesion usually remains visible for more than 12 months, which is taken to be permanent. If so, the dyspigmentation score is doubled. The scores are calculated

by simple addition based on the extent of the symptoms. The CLASI is designed as a table where the rows denote anatomical areas, while the columns score major clinical symptoms. The extent of involvement for each of the skin symptoms is documented according to specific anatomic areas that are scored according to the worst affected lesion within that area for each symptom.

A CLASI response is defined as  $\geq 50\%$  improvement of CLASI activity score from baseline.

[figure not shown]
### **Lupus Low Disease Activity State (LLDAS)**

A subject achieves LLDAS response if all of the following criteria are met:

1. hSLEDAI  $\leq 4$  with no activity in major organ systems (renal [proteinuria, haematuria, pyuria, urinary casts], central nervous system (CNS) [seizure, psychosis, organic brain syndrome, cranial nerve disorder, CVA], cardiopulmonary [pericarditis, pleurisy], vasculitis, fever)
2. no new lupus disease activity (i.e. no new descriptor scores in hSLEDAI) compared with the previous assessment
3. PGA VAS (scale 0-3)  $\leq 1$
4. Current prednisolone (or equivalent) dose  $\leq 7.5$  mg/day
5. Standard maintenance doses of immunosuppressive drugs and approved biological agents (i.e. no increase or initiation of immunosuppressive drugs).

### **BILAG Flare Index**

The BILAG flare index will be derived from BILAG 2004, as measured by BILAG score designation of “worse” or “new” resulting in a B score in  $\geq 2$  organs or an A score in  $\geq 1$  organ at one visit (Gordon et al, 2003) compared with the previous available assessment.

### Anti-dsDNA

**Anti-dsDNA is categorized as negative, indeterminate or positive as follows:**

**Positive:** > 15 IU/mL for subjects in Asia (Japan, Hong Kong, Taiwan and South Korea) and > 75 IU/mL for all other subjects.

**Indeterminate:** 10 - 15 IU/mL for subjects in Asia (Japan, Hong Kong, Taiwan and South Korea) and 30 - 75 IU/mL for all other subjects.

**Negative:** < 10 IU/mL for subjects in Asia and < 30 IU/mL for all other subjects.

